## Appendix 5. Blood and CSF Sampling Summary

### Protocol I9F-MC-SCAA Blood Sampling Summary (Part A – 43 Periods)

Purpose	Maximum Blood Volume Per Sample (mL)	Maximum Number of Blood Samples	Maximum Total Volume (mL)
Screening tests a	25	1	25
Clinical laboratory tests (central) a	5	<del>16</del> 12	<del>80</del> 60
Clinical laboratory tests (local lab)	12.5	<del>43</del>	<del>503</del> 7.5
LY3323795 plasma PK b	2	<del>60</del> 45(+5)	<del>120</del> 90 (10)
PD plasma samples b	2	<del>60</del> 45(+5)	<del>120</del> 90 (10)
Storage plasma samples	2	<del>60</del> 45	<del>120</del> 90
Blood discard for cannula patency	1	<del>44</del> 33	<del>44</del> 33
Pharmacogenetics	10	1	10
Total			<del>569</del> ( <del>589</del> ) 435.5 (455.5)
Total for clinical purposes [rounded up to nearest 10 mL]			<del>570</del> ( <del>590</del> ) 440 (460)

Abbreviations: PD = pharmacodynamics; PK = pharmacokinetics.

a Additional samples may be drawn if needed for safety purposes.

b A maximum of 5 additional plasma samples per subject may be drawn during the study at the discretion of the investigator or sponsor.

Statistical Analysis Plan: I9F-MC-SCAA

Single-Ascending Dose Study to Assess the Safety, Tolerability, Pharmacokinetics, and Pharmacodynamics of LY3323795 in Healthy Subjects

NCT02989389

Approval Date: 20-Dec-2016

**1. Statistical Analysis Plan:
I9F-MC-SCAA: Single Ascending Dose Study to Assess
the Safety, Tolerability, Pharmacokinetics, and
Pharmacodynamics of LY3323795 in Healthy Subjects**

Confidential Information

The information contained in this Statistical Analysis Plan (SAP) is confidential and the information contained within it may not be reproduced or, otherwise, disseminated without the approval of Eli Lilly and Company or its subsidiaries. This document and its associated attachments or appendices are subject to United States Freedom of Information Act (FOIA) Exemption 4.

LY3323795

A Phase 1 study of LY3323795 in healthy subjects that will be conducted in 3 parts. Parts A and B are subject- and investigator-blind, placebo-controlled, randomized studies. Part A is a single ascending dose, 3-period, 2-cohort, crossover study to assess the safety, tolerability, and plasma pharmacokinetics (PK) and pharmacodynamics (PD) of LY3323795 in healthy volunteers. Part B is a single-dose, 3-cohort study to assess the safety, tolerability, and the plasma and cerebrospinal fluid (CSF) PK and PD of LY3323795. Part C is an open label, 2-period, fixed-sequence study in healthy volunteers to evaluate a potential cytochrome P450 (CYP) 3A4 interaction when LY3323795 is coadministered with itraconazole.

Eli Lilly and Company
Indianapolis, Indiana USA 46285

Phase 1 Statistical Analysis Plan electronically signed and approved by Lilly on date provided below.

Approval Date: 20-Dec-2016 GMT

2. Table of Contents

| Section | Page |
|--|------|
| 1. Statistical Analysis Plan: I9F-MC-SCAA: Single Ascending Dose Study to Assess the Safety, Tolerability, Pharmacokinetics, and Pharmacodynamics of LY3323795 | 1 |
| 2. Table of Contents..... | 2 |
| 3. Revision History..... | 4 |
| 4. Objectives..... | 5 |
| 4.1. Primary Objective | 5 |
| 4.2. Secondary Objectives..... | 5 |
| 4.3. Exploratory Objectives..... | 5 |
| 5. Summary of Study Design | 6 |
| 5.1. Determination of Sample Size..... | 6 |
| 5.2. Method of Assignment to Treatment | 7 |
| 6. A Priori Statistical Methods | 8 |
| 6.1. General Considerations | 8 |
| 6.2. Multicenter Studies | 8 |
| 6.3. Multiple Comparisons/Multiplicity..... | 8 |
| 6.4. Patient Disposition | 8 |

4.1. Primary Objective

The primary objective of this study is to explore the safety and tolerability of single doses of LY3323795 in healthy subjects.

4.2. Secondary Objectives

The secondary objectives of this study are:

- To explore the plasma and cerebrospinal fluid (CSF) pharmacokinetics (PK) of single doses of LY3323795.
- To explore the plasma and CSF pharmacodynamics (PD) of single doses of LY3323795.

4.3. Exploratory Objectives

The logo for CCI (Clinical Care Innovations) is displayed in red text on a black rectangular background. The letters 'C', 'C', and 'I' are large and bold, with the 'I' being a vertical bar.

5. Summary of Study Design

Study I9F-MC-SCAA (SCAA) is a Phase 1 study in healthy subjects that will be conducted in 3 parts, as follows:

- Part A will be a subject- and investigator-blind, placebo-controlled, randomized, single ascending dose, 3-period, dose-escalation study to evaluate safety, tolerability, and plasma PK/PD of LY3323795.
- Part B will be a subject- and investigator-blind, placebo-controlled, randomized, single-dose, single-period, lumbar catheter study with up to 3 cohorts/dose levels to evaluate the central and plasma PK/PD of LY3323795.
- Part C will be an open-label, 2-period, fixed-sequence, single-cohort study to evaluate a potential cytochrome P450 (CYP) 3A4 interaction when LY3323795 is coadministered with itraconazole.

5.1. Determination of Sample Size

The sample size of 9 in each cohort of Part A is customary for Phase 1 studies evaluating safety, PK, and/or PD parameters, and is not based on statistical mean estimation.

For Part B, given the CSF $A\beta$ variability observed in prior studies that measured CSF $A\beta$, the sample size of 5 subjects per LY3323795 dose and 2 subjects per placebo in a parallel cohort, pooled placebo design is sufficient to detect a mean $A\beta$ reduction of approximately 21% or more from baseline. Assuming a standard deviation of 22% for the CSF $A\beta_{1-40}$, a sample size of 5 subjects per dose would provide approximately 90% coverage probability that the half-width of the 80% confidence interval (CI) for the mean of percentage change from baseline of CSF $A\beta_{1-40}$ would be within 21%. For example, if the estimate of the percentage change from baseline CSF $A\beta_{1-40}$ at nadir concentration (C_{nadir}) is 50%, then the confidence limit for the percentage change from baseline would be (29%, 71%).

For Part C, assuming a within-subject variability of 25% for the PK parameter (area under the drug plasma concentration versus time curve [AUC] or maximum concentration [C_{max}]) of LY3323795, a sample size of 8 subjects would provide approximately 90% coverage probability that the half-width of the 90% CI for the geometric mean ratio of LY3323795 with itraconazole, compared with LY3323795 alone, would be within 0.3 in log scale, or 1.35 in natural scale. For example, if the estimate of the ratio of LY3323795 with itraconazole over LY3323795 alone is 1.2, then the confidence limit would be (88%, 162%).

Subjects who drop out may be replaced at the discretion of the sponsor and investigator to achieve protocol-required completers. In Part A, a replacement subject's treatment assignment will follow that of the subject being replaced but may not require completion of all study periods. In Part B, a replacement subject's treatment assignment will follow that of the subject being replaced. In Part C, all subjects, and any replacements, will be on the same treatment assignment.

5.2. Method of Assignment to Treatment

For Cohorts 1 and 2 in Part A, up to approximately 24 subjects may be enrolled so that approximately 18 subjects (9 subjects per cohort [6:3, LY3323795:placebo per dose level]) complete the study.

For Cohorts 3 to 5 in Part B, up to approximately 30 subjects may be enrolled so that approximately 21 subjects (7 subjects per cohort [5:2, LY3323795:placebo]) complete the study.

For Cohort 6 in Part C, up to 12 subjects may be enrolled so that approximately 8 subjects complete the study. Part C is open label study.

Randomization tables for allocation of LY3323795 and placebo will be prepared by the Lilly statistician.

6. A Priori Statistical Methods

6.1. General Considerations

Statistical analysis of this study will be the responsibility of Eli Lilly and Company or designee.

It is planned that all safety reporting including eye safety assessments will be conducted by Covance; with the exception of inferential analyses on safety, PK, PD, and biomarkers, which will be conducted by Eli Lilly and Company.

Pharmacokinetic and pharmacodynamic analyses will be conducted on the full analysis set. This set includes all data from all subjects receiving at least 1 dose of the investigational product. Safety analyses will be conducted for all enrolled subjects, whether or not they completed all protocol requirements.

Additional exploratory analyses of the data will be conducted as deemed appropriate. As this is a Phase 1 study and there will be no formal statistical hypothesis testing, any changes to the planned analysis will not necessitate a protocol amendment and will be detailed in the study report.

Unless otherwise stated, all tests of treatment effects will be conducted at a 2-sided alpha level of 0.10 (0.05 each side).

6.2. Multicenter Studies

Due to this being a primarily safety and tolerability study with as single investigation center and low patient numbers per dose, there is no plan to fit center as a covariate in any of the models.

The demographic/disposition listings will make it clear as to which site each patient was attributed.

6.3. Multiple Comparisons/Multiplicity

No adjustments for multiplicity will be made.

6.4. Patient Disposition

All patients who discontinue from the study will be identified, and the extent of their participation in the study will be reported. If known, a reason for their discontinuation will be given.

6.5. Patient Characteristics

The patient's age, sex, race, weight, body mass index (BMI), height, smoking habits, or other demographic characteristics will be recorded and may be used in the PK, PD, and safety analyses as quantitative or classification variables. These characteristics will be listed and summarized at baseline, with the exception of weight which will also be summarized over time.

6.5.1. Subgroup Analyses

Any subgroup analyses will be exploratory (post hoc) in nature.

6.6. Concomitant Therapy

Concomitant therapy will be listed and summarized.

6.7. Extent of Exposure

Dosing information for each individual subject will be listed.

6.8. Safety Analyses

6.8.1. Clinical Evaluation of Safety

All investigational product and protocol procedure AEs will be listed, and if the frequency of events allows, safety data will be summarized using descriptive methodology.

The incidence of symptoms for each treatment will be presented by severity and by association with investigational product as perceived by the investigator. Symptoms reported to occur prior to randomization will be distinguished from those reported as new or increased in severity during the study. Each symptom will be classified by the most suitable term from the Medical Dictionary for Regulatory Activity (MedDRA).

The number of investigational product–related serious adverse events (SAEs) will be reported.

A listing of all patients' laboratory values and a listing of abnormal laboratory values (for that parameter) during the treatment period will be provided, and results will be summarized.

6.8.2. Statistical Evaluation of Safety

The safety analyses will be conducted for Part A, B, and C separately. The safety and tolerability of treatment will be assessed by summarizing the following:

- Adverse Events
 - Treatment-emergent adverse events (TEAEs) by:
 - System Organ Class (SOC) and Preferred Term (PT)
 - Maximum severity
 - Considered to be related to investigational produce by investigator
 - Serious Adverse Events (SAEs)
 - Adverse events (AEs) leading to discontinuation
- Vital signs and weight
- Laboratory measurements
- Electrocardiograms (ECGs)
- Eye assessments

Safety parameters will be listed and summarized using standard descriptive statistics, where appropriate. Additional analysis will be performed, if warranted, upon review of the data.

6.8.2.1. Adverse Events

Treatment-emergent adverse events are defined as the reported AEs that first occurred or worsened during the postbaseline phase, compared with baseline phase. For each TEAE, the severity level of the event (mild, moderate, or severe) will be determined by patient or physician opinion. The MedDRA Lowest Level Term (LLT) will be used in the treatment-emergent computation. For each LLT, the maximum severity at baseline will be used as the baseline severity. If the maximum severity during postbaseline is greater than the maximum baseline severity, the event is considered to be treatment-emergent for the specific postbaseline period. For each patient and TE AE, the maximum severity for the MedDRA level being displayed (PT, High Level Term [HLT], or SOC) is the maximum postbaseline severity observed from all associated LLTs mapping to that MedDRA level. For events that are gender-specific, the denominator and computation of the percentage will include only patients from the given gender.

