### **5.1.2. Part B: CSF Sampling Study**

Part B is a single-dose, 3-cohort (5:2 subjects, LY3323795:placebo per cohort), single-period, lumbar catheter study to evaluate central PK/PD of LY3323795. See Section 5.2 for planned enrollment numbers. Part B may be conducted in parallel to Part A of the study, as long as the conditions have been met for each dose decision in Part B (see Section 5.1.2.1).

Subjects will be admitted to the CRU on Day -1 and will remain as inpatients until at least 24 hours after the CSF catheter is removed, after which they may be discharged at the discretion of the investigator. CSF will be collected from an indwelling catheter using a closed system. The catheter will be inserted approximately 4 hours prior to study drug administration. CSF samples will be taken during this “stabilization” period approximately every 2 hours, as feasible. If some samples during the stabilization period are not collected for any reason, this will not be considered a protocol violation.

CSF PK and PD data will be collected by frequent sampling for 4 hours predose and up to 36 hours postdose (as described in the Part B Schedule of Activities, Section 2). The minus 4-hour CSF sample will be collected for safety (red blood cell count, glucose, and protein, to be tested at the local laboratory) and PD biomarkers (which will be tested centrally). The minus 2-hour sample will be collected for PD biomarkers only; the 0-hour and subsequent postdose samples will be collected for LY3323795 concentration and PD biomarkers. An additional safety CSF sample will be collected at the removal of the catheter. CSF PD samples will be split and stored

CCI

Plasma PK and PD (plasma A $\beta$ ) data will be collected up to 144 hours postdose (as described in the Part B Schedule of Activities, Section 2).

Safety assessments including clinical laboratory tests, ECGs, AEs, vital signs, ophthalmic examinations, and neurological surveys will be collected (as described in the Part B Schedule of Activities, Section 2).

Two IAD reviews are planned in Part B: the first after the completion of dosing for Cohort 3 and the second after dosing for Cohort 4. All CSF PK/PD data will be included in these reviews, as well as plasma PK data through Day 4. See Section 5.1.2.1 for details.

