investigator	A person responsible for the conduct of the clinical trial at a trial site. If a trial is conducted by a team of individuals at a trial site, the investigator is the responsible leader of the team and may be called the principal investigator.
IRB	institutional review board
LC/MS/MS	liquid chromatography with tandem mass spectrometry
Legal Representative	An individual or judicial or other body authorized under applicable law to consent, on behalf of a prospective subject, to the subject's participation in the clinical trial.
LP	lumbar puncture
MTD	maximum tolerated dose
NOAEL	no-observed-adverse-effect level
non-investigational product	A product that is not being tested or used as a reference in the clinical trial, but is provided to subjects and used in accordance with the protocol, such as: concomitant or rescue/escape medication for preventative, diagnostic, or therapeutic reasons, medication to ensure adequate medical care, and/or products used to induce a physiological response.
open-label	A study in which there are no restrictions on knowledge of treatment allocation, therefore the investigator and the study participant are aware of the drug therapy received during the study.
PK/PD	pharmacokinetic(s)/pharmacodynamic(s)
QTc	QT corrected for heart rate
RDA	recommended dietary allowance
SAE	serious adverse event
CCI	
screen	The act of determining if an individual meets minimum requirements to become part of a pool of potential candidates for participation in a clinical trial.
SUSAR	suspected unexpected serious adverse reaction
tmax	time to C max

CCI

tnadir	time to reach C nadir
treatment-emergent adverse event	Any untoward medical occurrence that emerges during a defined treatment period, having been absent pretreatment, or worsens relative to the pretreatment state, and does not necessarily have to have a causal relationship with this treatment
ULN	upper limit of normal

---

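### As worded, SAP 6.8.2.1 lets an event that is not treatment-emergent set the severity displayed for a TEAE at PT, HLT or SOC level

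*SAP*

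**What the plan says.** SAP 6.8.2.1 works in two steps.

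- **Which events are treatment-emergent.** The unit is the LLT: "The MedDRA Lowest Level Term (LLT) will be used in the treatment-emergent computation". The comparator is that term's own history: "For each LLT, the maximum severity at baseline will be used as the baseline severity". The test is a strict increase: "If the maximum severity during postbaseline is greater than the maximum baseline severity, the event is considered to be treatment-emergent". An LLT whose severity is unchanged or lower after baseline therefore fails the test.
- **What severity is displayed.** "For each patient and TE AE, the maximum severity for the MedDRA level being displayed" (PT, HLT or SOC) "is the maximum postbaseline severity observed from all associated LLTs mapping to that MedDRA level".

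SAP 6.8.2 plans TEAE summaries by SOC and PT and by maximum severity, so the second step feeds a planned output. HLT is named only in 6.8.2.1.

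Two other places bear on the point. SAP 6.8.1 undertakes to separate symptoms that predate randomization from those that appear or get worse later. Protocol Appendix 1 describes a TEAE as an occurrence "having been absent pretreatment, or worsens relative to the pretreatment state".

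**The concern.** The two steps use different sets of events. The first keeps only LLTs that rose above their own baseline. The second takes a maximum over every LLT in the PT or SOC, including those the first step rejected. The severity attached to a genuine TEAE can then come from an event that was already present and did not worsen. That also works against the separation of old from new symptoms promised in SAP 6.8.1.

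What is at stake is the reading of the maximum-severity table in a small first-in-human study. Part B is the most plausible setting. "The catheter will be inserted approximately 4 hours prior to study drug administration", and Protocol 3.3 names headache as the most common side effect of the procedure. A procedural complaint could begin before dosing and continue unchanged while a new, milder event in the same SOC appears. This requires that the pre-dose event counts as baseline; SAP 6.8.2.1 does not say where the baseline phase ends.

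**Working it through.** The plan gives no figure on this point, so there is none to reproduce. The check applies the written rule to every possible case of two LLTs in one PT or SOC.

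**Inputs** (all from SAP 6.8.2.1). Severity is none, mild, moderate or severe (0 to 3). Each LLT has a baseline maximum b and a postbaseline maximum p. It is treatment-emergent if p > b.

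**Two versions of the displayed severity**
- As worded: the maximum of p over all LLTs in the level.
- Restricted: the maximum of p over LLTs with p > b only.

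The restricted version takes the maximum over a subset, so the wording can never give a lower severity than the restricted rule. Any discrepancy is upward.

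**Count**
- Patterns for two LLTs: 4 × 4 × 4 × 4 = 256.
- For one LLT, 6 of the 16 (b, p) pairs have p > b and 10 do not. Patterns with at least one treatment-emergent LLT: 256 − 10 × 10 = 156.
- The versions differ only when one LLT is emergent, the other is not, and the other has the higher postbaseline severity. There are five such cases:

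| Emergent LLT | Non-emergent LLT | As worded | Restricted |
|---|---|---|---|
| none → mild | moderate → moderate | moderate | mild |
| none → mild | severe → moderate | moderate | mild |
| none → mild | severe → severe | severe | mild |
| none → moderate | severe → severe | severe | moderate |
| mild → moderate | severe → severe | severe | moderate |

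- Either LLT can be the emergent one, so 5 × 2 = 10 of the 156 patterns differ. In 8 the non-emergent event is unchanged; in 2 it improved from severe to moderate and still raises the label.

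These are counts of logical patterns. They say when the rule misfires, not how often it will.

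**Size of one occurrence.** Part B has 5 active subjects per dose, so one reclassified subject moves 1/5 = 20 percentage points from one severity row to a higher one. In Part A, with 6 active subjects per dose, it is 1/6 = 16.7 points.

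**What does not move.** In all 10 patterns the subject already has a real TEAE in that PT or SOC, so the subject is counted once under either version and TEAE incidence is the same. Seriousness is defined separately in Protocol 9.2.1. The stopping rules in Protocol 7.4.1 rest on related SAEs, related moderate or severe events, clinically significant events, ophthalmic findings and QTc readings, not on this table.

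**The case against.** The best reply is that the sentence opens with "For each patient and TE AE, the maximum severity for the MedDRA level being displayed". The thing being scored is a TEAE, so the associated LLTs may be meant as those belonging to that TEAE. The table is also planned as a table of TEAEs. On that reading an unchanged event never enters. This is a possible intention, but the sentence goes on to take in every LLT that maps to the displayed level, and no other section narrows it. Even if the narrow meaning was intended, two programmers could produce different tables from the same text.

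The reply is right about the limits. Product and procedure AEs are also listed individually, so a reader can trace an odd severity entry in a seven-subject cohort. Subjects are healthy, and Part B excludes clinically significant back pain and pathology that might complicate lumbar puncture. The effect also needs a rare combination: a moderate or worse event that predates dosing, continues without worsening, and exceeds in severity every TEAE in the same PT or SOC.

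Three stronger readings are tempting, and the documents do not support them.

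- A reader might infer that the rule contradicts the protocol's TEAE definition. Appendix 1 settles which events are TEAEs and is silent on displayed severity. The old event is not itself counted as a TEAE under either version.
- A reader might infer that the primary endpoint is distorted. That endpoint is TEAE incidence, which is unaffected.
- A reader might infer a bias against LY3323795, or a high rate of misclassification in Part B. Parts A and B are randomized against placebo, so pre-dose catheter events should balance in expectation. Neither document gives the frequency of such events, so any rate would be only the product of assumed inputs.

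**Conclusion.** The point holds as a minor defect of wording in a stated rule. On its plain reading, SAP 6.8.2.1 can label a mild TEAE moderate or severe, or a moderate one severe, because of an event that is not treatment-emergent. This does not fit the rule earlier in the same paragraph or the intent of SAP 6.8.1. The direction is always upward, and only the descriptive TEAE-by-maximum-severity summary is affected. It is likeliest at SOC level, where many LLTs pool. It should be uncommon, and its frequency cannot be estimated from the documents; one instance is 20 points of a severity row in a Part B dose group.

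The conclusion rests on two conditions: that the sentence is programmed as written, and that the earlier event is recorded with a postbaseline severity. An event that resolved before dosing has no effect.

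**What to change.** In the maximum-severity sentence of SAP 6.8.2.1, insert the word treatment-emergent before LLTs, so that the displayed severity is drawn only from terms that passed the LLT-level test. If the maximum over all LLTs is really intended, the SAP should say so and the table should carry a footnote.

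The cost is a one-word SAP edit and one filter in the adverse event program. No new data are needed. The only visible consequence is that some moderate or severe counts may be slightly lower.
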